6.2 Study Management Plan

The Data Management Center (DMC) will maintain a web page informing sites as to the availability of enrollment slots per cohort. The protocol team, including the co-chairs, medical officers, pharmacist, and pharmacologist, will respond to sites who contact the team with questions regarding toxicity management, dosing, or other issues within one business day. Team responses will include the entire team.

Sites will be given 7 days to respond to queries to allow the team to meet Merck data delivery requirements. Sites will be contacted by the protocol data manager or co-chairs regarding any query responses or data issues that are outstanding after 7 days.

All RAL dose modifications will be recommended by the protocol team. See Section 6.21 for information on dose modifications for Cohorts 1 and 2. The protocol team will review the PK data for each participant as part of an on-going evaluation of the dosing regimen to determine whether a dose adjustment is required. The study team will conduct an extensive review of the data obtained from participants enrolled in Cohort 1 before opening enrollment for Cohort 2. Dose recommendations for Cohort 2, and supporting dose finding data from Cohort 1, must be approved by the Medical Officers, IMPAACT representatives and Merck representatives. If all agree, Cohort 2 opens to enrollment. If there is disagreement among IMPAACT, Merck and/or the study team, a Study Monitoring Committee (SMC) will be

appointed to review the data understanding that Cohort 2 will not open without Merck approval. See Section 8.51 for more details on SMC monitoring of study data and progress.

The P1110 team will notify sites of any change in dose and/or dosing frequency through an appropriate mechanism. Dosing tables found in Appendix III will be used for dosing changes and are based on weight bands.

6.21 Cohort Dosing Management

Cohort 1

A minimum of 12 neonates will be enrolled into Cohort 1 to provide data for 12 PK evaluable neonates. All neonates enrolled in Cohort 1 will receive, per Section 5.11, oral granules for suspension as two separated single doses, the first given within 48 hours of birth and a second dose administered at 7 to 10 days of life, with PK assessed after each dose. The PK results and safety will be assessed through the regular team monitoring (done at least every 4 weeks) and at full cohort accrual to ensure that the RAL concentrations in each individual do not exceed a C_{max} of 19,630 nM (8,720 ng/mL) and do not exceed an AUC₁₂ of 63,050 nM-hr (28,000 ngxh/mL), and that no life-threatening toxicities probably related to RAL administration have occurred.

Based on the team assessment of the PK data and review of safety information, the dose may be modified for the subsequent participants receiving the 2 doses in Cohort 1, in which RAL dosing may be modified in the range of 1.5 mg/kg to 6 mg/kg per dose.

Cohort 2

After enrollment of participants into Cohort 1 RAL-exposed or RAL-naïve group is completed with acceptable safety and an appropriate multiple dose regimen from birth to 6 weeks is determined, Cohort 2 will open for the respective group. The initial multiple dose regimen for Cohort 2 may be determined based on results from P1097, P1110 Cohort 1, P1066 (Cohorts IV and V), P1026s, and PK modeling and simulation. The PK targets for Cohort 2 are geometric mean target exposures for:

- once-daily dosing of AUC₂₄ of 28-90 μMxhr (12-40 mgxh/L) and an approximate GM trough (C_{24hr}) > 75nM (33ng/mL)
- twice-daily dosing of AUC₁₂ of 14-45 μMxhr (6-20 mgxh/L) and an approximate GM trough (C_{12hr}) > 75nM (33ng/mL)

A minimum of 20 neonates will be enrolled into Cohort 2 to provide data for 20 PK evaluable infants. The dosing for RAL is further detailed in Section 5.11 of this protocol.

Cohort 2 dosing may be modified based on observed pharmacokinetic data coupled with modeling and simulation to determine the optimal multiple dose regimen capable of meeting the selected PK targets: If the minimum targets above are not achieved, the dose will be increased in linear fashion.

6.3 Criteria for Treatment Discontinuation

The participant will have study drug discontinued for the following reasons:

- 6.31 The participant requires treatment with medications that are disallowed while on this study.
- 6.32 The participant experiences dose limiting or intolerable drug toxicity as defined in Section 6.1.
- 6.33 New data become available that indicate treatment should be discontinued.
- 6.34 It is determined by the study team or the treating healthcare providers that continued study treatment with RAL is not in the best interest of the participant and the participant will be followed off study treatment on study.

6.4 Permanent Study Discontinuation

The participant will be discontinued from the study for the following reasons:

- 6.41 The parent or legal guardian refuses further treatment and/or follow-up evaluations.
- 6.42 The investigator determines that further participation would be detrimental to the participant's health or well-being.
- 6.43 The parent or legal guardian fails to comply with the study requirements so as to cause harm to the participant or seriously interfere with the validity of the study results.

The study may be discontinued at any time by the IMPAACT network, the Office for Human Research Protections (OHRP), the National Institutes of Health (NIH), the local IRB or EC, U.S. Food and Drug Administration (FDA), the pharmaceutical sponsors, or other governmental agencies.

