4.0 SELECTION AND ENROLLMENT OF PARTICIPANTS

4.1 Maternal Inclusion Criteria

- 4.11 Mother is either known to be HIV-1 infected prior to labor or identified as HIV-1 infected at the time of labor or in the immediate postpartum period.

Documentation of HIV infection:

Documentation of HIV-1 infection is defined as positive results from two samples (whole blood, serum, or plasma) collected at different time points. Results documented in the clinical record from past testing may be used to satisfy the criteria for documentation of HIV-1 infection.

If both samples are tested using antibody tests, at least one of the samples must be tested in a laboratory that operates according to Good Clinical Laboratory Practice (GCLP) guidelines and participates in an appropriate external quality assurance program. If nucleic acid testing is used, at least one test must be performed in a CLIA-certified (US sites) or VQA-certified (non-US) laboratory. For tests performed in other (non-GCLP-compliant or non-VQA-certified) settings, adequate source documentation including the date of specimen collection, date of testing, test performed, and test result must be available.

Sample #1 must be tested using any of the following:

- Up to two rapid antibody tests from different manufacturers or based on different principles and epitopes.
- One EIA OR Western Blot OR immunofluorescence OR chemiluminescence
- One quantitative HIV RNA PCR (above the limit of detection of the assay)
- One HIV DNA PCR

- One qualitative HIV RNA PCR
- One total HIV nucleic acid test

Note: Confirmatory testing (Sample #2) may be pending at the time of enrollment of the mother-infant pair. If maternal confirmatory testing is negative, the infant will be removed from active dosing but will be followed for safety as part of the study.

Sample #2 must be tested using any of the following:

- Rapid antibody test. If this option is used in combination with two rapid tests for Sample #1, at least one of the three rapid tests must be FDA-approved, and the third rapid test must be from a third manufacturer or based on a third principle or epitope.
- One EIA OR Western Blot OR immunofluorescence OR chemiluminescence
- One quantitative HIV RNA PCR (above the limit of detection of the assay)
- One HIV DNA PCR
- One qualitative HIV RNA PCR
- One total HIV nucleic acid test

4.12 For Cohort 1 and Cohort 2 (RAL-naive): Mother is at high-risk of transmitting HIV to infant as evidenced by any of the following:

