5.13 Duration

Cohort 1 will receive two single observed doses of RAL oral granules that are prepared by site staff in addition to standard of care ARV for PMTCT prophylaxis. The first dose should be within 48 hours of birth and the second single dose at 7 to 10 days of life.

Cohort 2 will receive 6 weeks of RAL oral granules in addition to standard of care ARV for PMTCT prophylaxis.

Participants will be followed for 24 weeks after birth.

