Grade 3 - Continue RAL while awaiting confirmatory results unless the clinician believes that remaining on RAL would be unsafe. Other PMTCT antiretroviral prophylaxis may be continued pending confirmatory testing.

If Grade 3 abnormalities are confirmed, contact the study team, and the RAL should be withheld and other antiretroviral drugs used for PMTCT prophylaxis should be held until the abnormalities are Grade 2 or below unless the clinician, with the approval of the study team and medical officer, believes that the event is unlikely related to RAL administration and/or that PMTCT prophylaxis should be continued.

Grade 4 – Contact the study team. Hold RAL and concomitant antiretrovirals used for PMTCT immediately unless the clinician, with the approval of the study team and medical officer, believes that withholding antiretroviral prophylaxis (including RAL) would be harmful to the patient and that continuing them would pose little additional risk. Attempt to confirm any unexpected laboratory results as soon as possible, within 72 hours of awareness of the event. The protocol team should be notified of the results at [contact].

For confirmed drug related Grade 4 SADR, RAL should be permanently discontinued. For Grade 4 adverse events that are determined to be unrelated to study drug, the investigator should contact the team to determine when RAL may be safely resumed.

*NOTE: In the event of treatment discontinuation, participants will be asked to continue to be followed until the 24 week visit.

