6.13 Bilirubin Management

Due to the potential for interactions between RAL and bilirubin affecting RAL pharmacokinetics and bilirubin elimination and toxicity (see Section 1.27) special management procedures for bilirubin will be used. Bilirubin concentrations and interventions to lower bilirubin (such as phototherapy and exchange transfusion) will be recorded but bilirubin will be graded according to the DAIDS Toxicity Table and

managed according to the schema described below. Hyperbilirubinemia will be managed by clinical caregivers according to local standards of care. If total bilirubin is >16.0 mg/dL or an exchange transfusion is performed, no further RAL doses will be administered but participants will continue to be followed for safety assessments. Participants who receive phototherapy may continue to receive study drug as long as total bilirubin concentration \leq 16.0 mg/dL.

The protocol team must be notified if study drug is held due to elevated bilirubin or of Grade 3 or 4 hyperbilirubinemia determined to be at least possibly related within 24 hours of site awareness at [contact].

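### Section 6.41 makes a parent's refusal of raltegravir alone a mandatory study exit, although the protocol otherwise follows infants who stop the drug; if applied, primary-window safety labs and HIV tests are lost

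*Protocol*

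**What the plan says.** Section 6.4 (Permanent Study Discontinuation) opens with "The participant will be discontinued from the study for the following reasons", and item 6.41 reads "The parent or legal guardian refuses further treatment and/or follow-up evaluations". Section 5.0 defines study treatment as raltegravir only.

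Section 6.3 is the separate list for stopping drug without leaving the study. It opens with "The participant will have study drug discontinued for the following reasons" and covers disallowed medication, toxicity, new data, and a decision by the team or treating provider. It does not mention refusal by a parent.

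Elsewhere, infants who stop RAL remain under follow-up:

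- Section 4.11, negative maternal confirmatory test: "the infant will be removed from active dosing but will be followed for safety as part of the study".
- Section 6.12, a note under both cohorts: "In the event of treatment discontinuation, participants will be asked to continue to be followed until the 24 week visit".
- Section 6.13, bilirubin stop or exchange transfusion: "no further RAL doses will be administered but participants will continue to be followed for safety assessments".
- Section 6.34, team or provider decision: "the participant will be followed off study treatment on study".
- Section 5.13, in general: "Participants will be followed for 24 weeks after birth".

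The letter of amendment and the two clarification memoranda at the front of the protocol leave 6.41 unchanged.

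**The concern.** Stopping the drug and leaving the study are different events, and 6.41 merges them for one cause. A site whose parent says no more RAL but yes to visits finds that case named in only one list, and that list orders exit.

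Primary objective 1 is safety through 6 weeks of life. SAP 4.6 counts Grade 3 or 4 events and deaths with onset through day 49 in every infant who had at least one dose. Missing data are reported only as a footnote count. An infant taken off study early, with no event so far, therefore counts as a non-event whatever happens afterwards. The loss may also be informative, since a parent may refuse RAL because the infant seems unwell; that is plausible, but the documents do not say it.

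The 6- and 24-week HIV tests in Section 3.1 would be lost too, in infants enrolled because they are HIV-exposed. Under Section 7.4 the expedited reporting period ends when the participant leaves the study; after that, only passively learned SUSARs are reported.

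**Working it through.** **1. Do the provisions conflict?** The lead-in to 6.4 is mandatory, and with and/or in 6.41 refusal of treatment alone is sufficient. Sections 4.11, 6.13 and 6.34 show the protocol's intent but concern other causes, so they do not contradict 6.41. The 6.12 note and 5.13 are broad enough to contradict it directly. The 6.12 note, however, sits under toxicity management, and neither provision mentions parental refusal.

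**2. Scheduled assessments lost in Cohort 2.** Appendix II-B places laboratory draws at entry, after the second dose (bilirubin only), Day 6-9, Day 15-18, Day 28-32, 5-6 weeks, 8-10 weeks and 24 weeks. SAP Table 5 assigns the 5-6 week visit to days 34-49 and the 8-10 week visit to days 50-84. HIV nucleic acid tests fall at entry, 5-6 weeks and 24 weeks.

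| Exit just after | Lab visits lost | Of these, by day 49 | HIV tests lost |
|---|---|---|---|
| Second-dose visit | 6 | 4 | 2 |
| Day 6-9 | 5 | 3 | 2 |
| Day 15-18 | 4 | 2 | 2 |
| Day 28-32 | 3 | 1 | 2 |

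The Early Discontinuation column of Appendix II-B shows history and physical examination but no hematology, chemistry or HIV test. Section 3.0 says Cohort 2 labs are done at all study visits, so it is unclear whether exit labs are drawn. One exit draw would not replace the later visits in any case.

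**3. Effect on the primary proportion (illustration).** The one group still to enroll under this text is Cohort 2 RAL-exposed, minimum 8 (Section 8.4). The planned interval is the two-sided 90% Clopper-Pearson.

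- The plan's own figure for 0/8 is an upper limit of 0.37 (Table 14). That value is 1 − 0.025^(1/8) = 0.369, which is the 95% limit. The 90% limit is 1 − 0.05^(1/8) = 0.312, and it is used here.
- One event observed: 1/8 = 12.5%, 90% CI 0.6% to 47.1%.
- The same event unobserved after exit: 0/8 = 0%, 90% CI 0% to 31.2%.

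**4. Adherence (secondary).** SAP 4.5 divides actual days on RAL by expected days and takes the off-study date into account. Assume the first dose is on day 1 and expected days run to day 42 or the off-study date, whichever is earlier. For a last dose on day *s* and an off-study date *g* days later, adherence is *s*/(*s*+*g*). If the infant is followed instead, it is *s*/42.

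| Last dose | *g* = 0 | *g* = 3 | *g* = 7 | If followed |
|---|---|---|---|---|
| Day 7 | 7/7 = 100% | 7/10 = 70% | 7/14 = 50% | 7/42 = 17% |
| Day 14 | 14/14 = 100% | 14/17 = 82% | 14/21 = 67% | 14/42 = 33% |
| Day 28 | 28/28 = 100% | 28/31 = 90% | 28/35 = 80% | 28/42 = 67% |

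**The case against.** The strongest counter-argument is that the protocol already covers this case. The 6.12 note does not limit the cause of stopping, and asking families to stay suits a parent's choice. Section 5.13 promises 24 weeks of follow-up. The literal reading of 6.41 also sits oddly beside 6.43, which ends participation for non-compliance only when it causes harm or seriously threatens validity: a parent who openly declines RAL would be treated more harshly than one who quietly stops giving it. SAP 4.3 tabulates off-treatment and off-study reasons separately, so the analysis does not equate the two. This shows that sites may not apply 6.41 literally. It leaves them with conflicting instructions, of which the one that names refusal is the exit rule. The sample consent forms were not in the text examined, so what parents are told about stopping RAL cannot be checked.

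The second argument is that the effect is hypothetical and small. It needs a refusal of drug only, a site that applies 6.41, and a later unobserved Grade 3 or 4 event, all within one small group. An infant who exits before the Day 15-18 intensive sampling might be replaced for PK, which would raise the dosed number to at least 9 (1/9 = 11.1% in place of 12.5%). The primary safety analysis is descriptive. All of this stands as a limit on size, but replacement does not recover the lost observations.

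Several mitigations also stand. Events before exit are counted and followed (Section 6.14). The exit history records outside laboratory and HIV results up to that date (Appendix II-B, footnote 1). Deaths must be reported regardless of cause (Section 7.2). Reasons for stopping RAL are tabulated (SAP 4.3 and 4.5). None of these provides the scheduled labs or HIV tests due after exit.

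On adherence, truncating at the off-study date is stated openly in the SAP, applies to any exit, and does not affect a protocol endpoint. That part is a side effect and carries little weight here.

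**Conclusion.** The concern holds. As written, 6.41 makes refusal of RAL alone a mandatory exit, 6.3 offers no alternative for that cause, and the result departs from how the protocol treats infants who stop RAL for other reasons.

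If the rule is applied in Cohort 2 after the second-dose visit or later, it costs one to four scheduled laboratory visits inside the primary safety window, depending on when the infant exits, and both remaining HIV tests. Any bias in the Grade 3 or 4 proportion from events missed this way is downward.

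The expected size cannot be stated, because the documents give no refusal rate and it is not known how sites would read 6.41 against 6.12. The 1/8 versus 0/8 comparison assumes exactly one missed event among eight dosed infants. This is a correction that should be made because it is cheap and protects ascertainment of the primary safety endpoint; it does not invalidate the design.

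**What to change.** Reword 6.41 so that only refusal of further follow-up evaluations triggers study exit. Add an item to 6.3 for a parent or guardian who declines further study drug, stating that the infant stays on study off RAL through the 24-week visit, in line with 6.34.

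This is two sentences, in a short amendment or clarification. It adds no visit type, no sample size and no analysis: the extra work is completing visits already scheduled for these infants. Parents remain free to decline follow-up as well.

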7.0 EXPEDITED ADVERSE EVENT REPORTING

7.1 Adverse Event Reporting to DAIDS

Requirements, definitions and methods for expedited reporting of Adverse Events (AEs) are outlined in Version 2.0 of the DAIDS EAE Manual, which is available on the RSC website at <http://rsc.tech-res.com/clinical-research-sites/safety-reporting/manual>.

The DAIDS Adverse Experience Reporting system (DAERS), an internet-based reporting system, must be used for expedited AE reporting to DAIDS. In the event of system outages

or technical difficulties, expedited AEs may be submitted via the DAIDS EAE Form. For questions about DAERS, please contact NIAID CRMS Support at [contact]. Site queries may also be sent from within the DAERS application itself.

Where DAERS has not been implemented, sites will submit expedited AEs by documenting the information on the current DAIDS EAE Form. This form is available on the RSC website: <http://rsc.tech-res.com/clinical-research-sites/safety-reporting/manual>. For questions about EAE reporting, please contact the RSC ([contact]).

7.2 Reporting Requirements for this Study

The SAE Reporting Category, as defined in Version 2.0 of the DAIDS EAE Manual, will be used for this study.

The study agent for which relationship assessments are required is raltegravir.

In addition to reporting all SAEs as defined above, other events that sites must report in an expedited fashion include bilirubin concentrations >16.0 mg/dL, exchange transfusions for hyperbilirubinemia, all malignancies, seizures, IRIS events, and hepatotoxicities whether or not symptomatic or related to study drug, and all other Grade 3 or 4 related toxicities for which a relationship to study drug cannot be ruled out.

Over doses will be reported on a quarterly basis to the pharmaceutical sponsor.

The death of any participant after enrollment or within 30 days of study completion, regardless of the cause, must be reported within three business days of first becoming aware of the death. If an autopsy is performed, the report must be provided. Reports of all deaths must be communicated as soon as possible to the appropriate IRB or EC and/or reported in accordance with local law and regulations.

For all SAEs submitted to RSC, sites must file an updated SAE report to RSC with the final or stable outcome (Status Code p. 5 of the EAE form) unless the SAE reported in the initial EAE form already had a final or stable outcome.

7.3 Grading Severity of Events

The Division of AIDS Table for Grading the Severity of Adult and Pediatric Adverse Events (DAIDS AE Grading Table), Version 1.0, December 2004, Clarification August 2009, must be used and is available on the RSC website at <http://rsc.tech-res.com/clinical-research-sites/safety-reporting/daids-grading-tables>

7.4 Expedited AE Reporting Period

The expedited AE reporting period for this study is the entire study duration for an individual participant (from initial administration of study drug until study completion or discontinuation of the participant from study participation for any reason).

After the protocol-defined reporting period, unless otherwise noted, only SUSARS as defined in Version 2.0 of the EAE Manual will be reported to DAIDS if the study staff become aware of the events on a passive basis (from publicly available information).

8.0 STATISTICAL CONSIDERATIONS

8.1 General Design Issues

This is a Phase I multi-center, open label, non-comparative study to assess the safety and pharmacokinetics of raltegravir administered to full-term neonates, aged ≤ 48 hours (protocol Version 1.0) and ≤ 60 hours (protocol Version 2.), at risk of acquiring HIV-1 infection. The goal is to determine a dose of raltegravir, that is safe, well-tolerated and meets PK targets, administered as an oral granules suspension to neonates and infants in the first 6 weeks of life. Both the mother and the infant will be enrolled, with the mother having only a study entry visit and the infant followed through 24 weeks of life.

Safety data will include signs/symptoms, diagnoses and laboratory test results, which will include results of evaluations specified in the protocol and results from the infant's clinical care. Infants will be evaluable for safety analysis if they received at least one dose of raltegravir. For CRF reporting and analysis of safety data, the sites' assessments of AE relationship to raltegravir will be used. However, with regards to participant safety and PK evaluations which will support the selection of a dose for a given cohort, the protocol team will also have input as to the causality and drug relation of specific adverse experiences. Regular monitoring of RAL safety, which could result in dose or study modification, described in detail in Section 8.5.

Approximately 50 infants and their mothers will be enrolled in order to have a minimum of 12 and 20 PK evaluable participants in Cohorts 1 and 2, respectively. If a participant has unevaluable PK data, which reflects uncertainty about appropriate exposure to the study medication then the participant will be excluded from PK analyses and will be replaced.

The study design consists of two cohorts with the following dosing regimens of raltegravir in addition to standard PMTCT:

Cohort 1:

Raltegravir as oral granules for suspension, per Section 5.11 administered as a single dose within 48 hours of birth, with a second dose administered at 7-10 days of life

Cohort 2:

Raltegravir as oral granules for suspension, per Section 5.11 administered as daily dosing through 6 weeks of life with first dose given within 48 hours of birth for RAL-naïve infants and between 12 and 60 hours of birth for RAL-exposed infants.

Study accrual will initially be for Cohort 1 only with accrual to Cohort 2 contingent upon neonates in Cohort 1 successfully meeting the safety criteria and providing adequate information for Cohort 2 initial dosing. Initial dosing for Cohort 2 RAL-naïve and RAL-exposed groups will be determined using modeling and simulation analyses based on P1110 available data and data from IMPAACT P1097, P1066 (Cohorts IV and V) and P1026s.

Criteria for defining PK evaluable neonates, along with descriptions of PK parameters and analyses can be found in Section 9.

